### 7.8.2 **FPS-R**

Pain will be assessed in subjects 4 years of age or older using the FPS-R. Time to onset of symptom relief in this case will be defined as the duration of time in hours from the time of study drug administration to the earliest time at which the post-treatment score improves by at least one level. Subjects not achieving the onset of symptom relief for FPS-R will be censored at the time of their last FPS-R assessment. Time to onset of symptom relief will be summarized using the Kaplan-Meier method. Subjects with pretreatment value of zero will be excluded from this analysis.

Time to minimum symptom for FPS-R is defined as the duration of time in hours from the time of study drug administration to the earliest time at which the post-treatment score improves to zero (or no pain). Subjects not achieving minimum symptom for FPS-R will be censored at the time of their last FPS-R assessment. Time to minimum symptom for FPS-R

will be summarized using the Kaplan-Meier method. Subjects with pretreatment value of zero will be excluded from this analysis.

The observed values and change from pre-treatment in the FPS-R score will be summarized by study time-point.

Analyses on the FPS-R will be performed for the initial icatibant exposure and both subsequent icatibant exposures.

### 7.8.3 FLACC

For subjects less than 4 years of age, the investigator will assess HAE-related pain (cutaneous, abdominal, and laryngeal) using FLACC. Time to onset of symptom relief will be calculated from the time of study drug administration to the earliest time at least a 20% improvement is seen in the total post-treatment pain score. Subjects not achieving the onset of symptom relief for FLACC will be censored at the time of their last FLACC assessment. Time to onset of symptom relief will be summarized using the Kaplan-Meier method. Subjects with pretreatment value of zero will be excluded from this analysis.

Time to minimum symptom for FLACC is defined as the duration of time in hours from the time of study drug administration to the earliest time at which the post-treatment total score improves to zero (or no pain). Subjects not achieving minimum symptom for FLACC will be censored at the time of their last FLACC assessment. Time to minimum symptom for FLACC will be summarized using the Kaplan-Meier method. Subjects with pretreatment value of zero will be excluded from this analysis.

The observed values and changes from pre-treatment in the total pain score will be summarized by study time-point. Similarly, the scores in each of the five domains will be summarized by the study time-point.

Analyses on FLACC will be performed for the initial icatibant exposure only.

### 7.8.4 Other Efficacy Analyses

#### Time to First Use of Rescue Medication

The number and percentage of subjects who received rescue medications before the onset of symptom relief will be summarized. Time to first use of rescue medication prior to onset of symptom relief will be calculated from the time of study drug administration to the first use of rescue medication prior to the onset of symptom relief. Subjects not using rescue medication prior to the onset of symptom relief will be censored at the time of their onset of symptom relief. Time to first use of rescue medication will be summarized using the Kaplan-Meier method. This analysis will only be performed if there are at least 5 subjects for a given attack who used rescue medication prior to attaining symptom relief.

Subjects who received rescue medication before the onset of symptom relief will be denoted in the listing on rescue medication for the efficacy population.

Analyses on time to first use of rescue medication will be performed for the initial icatibant exposure and both subsequent icatibant exposures.

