10.8 Other Analyses

The number and percentage of subjects who received rescue medications before the onset of symptom relief will be summarized by the stratification group and icatibant exposure number. Time to first use of rescue medication prior to symptom relief will be calculated from the time of investigational product administration to the first use of rescue medication prior to the onset of symptom relief. The median time and the 95% confidence interval will be calculated using Kaplan-Meier methodology if there are at least 5 subjects for a given attack who used rescue medication prior to attaining symptom relief.

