## 4. STUDY DESIGN

### 4.1 General Description

This is an open-label, non-randomized, single-arm study to evaluate the PK, tolerability, and safety, including effects on reproductive hormones, of a single SC administration of icatibant in pediatric subjects with HAE.

The study enrolled children and adolescents from 2 to less than 18 years of age, divided into 2 groups: prepubertal (Tanner stage I) and pubertal/postpubertal (Tanner stages II to V).

After a qualifying screening period, the PK, safety/tolerability, and efficacy of treatment with SC icatibant was evaluated in at least 20 subjects (10 prepubertal and 10 pubertal/postpubertal subjects) who presented with cutaneous, abdominal, or laryngeal symptoms of an acute attack of HAE.

The PK and safety/tolerability of SC icatibant was evaluated in at least 10 additional pubertal/postpubertal subjects who met screening criteria, but received treatment with SC icatibant in the absence of a current acute HAE attack.

Subjects will receive treatment with a single SC administration of icatibant on Day 1 and will be monitored closely in the hospital/study center for at least 6 to 8 hours after treatment. Subjects will undergo PK and safety assessments; efficacy assessments will be performed if treatment occurs during an acute HAE attack. All subjects will have serum reproductive hormone measurements.

A subject may be discharged after completion of assessments at 6 hours post treatment, if deemed medically stable in the investigator's clinical judgment and, if applicable, the subject's HAE symptoms have resolved (the subject's investigator-rated symptom score must be zero, denoting the absence of symptoms). If HAE symptoms have not completely resolved at 6 hours (ie, the investigator-rated symptom score is >0), the subject shall remain in the hospital/study center for at least 8 hours after icatibant administration for further evaluation. Telephone follow-up will occur at both 24 and 48 hours after treatment. Subjects will return to the hospital/study center for scheduled assessments on Day 8 and for a follow-up visit on Day 90.

A table showing the Schedule of Events for the study is provided in [Appendix III: Schedule of Events](#).

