## 7. STATISTICAL ANALYSES

### 7.1 General Considerations

All statistical analyses will be performed using SAS® statistical software (SAS Institute, North Carolina, USA) except for the population PK modeling which will be performed with nonlinear mixed effect modeling software (eg, Phoenix NLME module, Pharsight Corp.). A separate analytic plan will be developed to support the analysis of PK data. The analysis methods for all other study data (demographic and pretreatment characteristics, efficacy variables, and safety variables) will be detailed in the SAP.

Data will be summarized with respect to disposition, demographic, pre-treatment characteristics, safety variables, and efficacy variables. Summary statistics for continuous variables will include the number of subjects, the mean, median, standard deviation, and range. For categorical data, summaries will include counts and percentages. Time-to-event data will be summarized using Kaplan-Meier estimates of the 25th, 50th (median), and 75th percentiles with associated 2-sided 95% confidence intervals, as well as percentage of censored observations. Plots of the Kaplan-Meier curves and supporting data listings detailing each subject's contribution to the analysis will be provided.

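### Time to first rescue is estimated by Kaplan-Meier with symptom relief treated as censoring; relief is a competing event, so the percentiles can overstate rescue use when the analysis is triggered

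*SAP*

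**What the plan says.** SAP 7.8.4, under Time to First Use of Rescue Medication, measures the time "from the time of study drug administration to the first use of rescue medication prior to the onset of symptom relief". For subjects who reach relief unrescued the rule is "Subjects not using rescue medication prior to the onset of symptom relief will be censored at the time of their onset of symptom relief". The estimator is then named: "Time to first use of rescue medication will be summarized using the Kaplan-Meier method". There is a trigger: "This analysis will only be performed if there are at least 5 subjects for a given attack", counting those rescued before relief.

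SAP 7.1 fixes what is reported: "Time-to-event data will be summarized using Kaplan-Meier estimates of the 25th, 50th (median), and 75th percentiles with associated 2-sided 95% confidence intervals", together with the percentage censored. Protocol 10.8 has the same analysis and trigger, with the median and its interval "calculated using Kaplan-Meier methodology if there are at least 5 subjects for a given attack who used rescue medication prior to attaining symptom relief", but gives no censoring rule.

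The same SAP subsection first plans a simple proportion: "The number and percentage of subjects who received rescue medications before the onset of symptom relief will be summarized". Neither document mentions cumulative incidence or competing risks, and SAP 9.7 plans no sensitivity analysis.

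**The concern.** The event is defined as rescue that comes before relief. A relieved subject can therefore never have the event. Kaplan-Meier treats a censored subject as still able to have it, at the same rate as those who remain at risk. Each relief shrinks the risk set without being counted as a final outcome, so every later rescue produces a larger step than it should.

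The resulting percentiles refer to a setting in which relief does not remove anyone from risk, and even that reading needs relief and rescue to be independent. Independence is doubtful, because subjects who respond poorly are both slow to get relief and likely to need rescue.

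At stake are Tables 14.2.7.1 and 14.2.7.2. They could print a median time to rescue, which implies that at least half the subjects were rescued, while the planned percentage shows a much smaller share. The table titles do not mention the restriction to rescue before relief, which makes a misreading easier.

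**Working it through.** The plan states no expected figure for this analysis, so there is nothing to reproduce. The check applies the planned estimator and the competing-risk estimator to the same data.

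**Inputs from the documents**
- First attack: efficacy "was evaluated in at least 20 subjects (10 prepubertal and 10 pubertal/postpubertal subjects") (SAP 4.1), so n = 20 is the planned minimum.
- Trigger: 5 rescues before relief in an attack (SAP 7.8.4). The smallest triggering share in a first attack is 5/20 = 25%.
- Median time to relief in the completed initial part: 1.0 h (Protocol 1.2.2). Many reliefs would therefore come before any later rescue.

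**Formulas.** At each time, n is the number at risk and d the number rescued.
- One minus Kaplan-Meier: 1 − ∏(1 − d/n), with reliefs leaving the risk set as censored.
- Aalen-Johansen: Σ S × d/n, where S is the proportion with neither rescue nor relief just before that time.

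**Late rescue (constructed data).** Fifteen subjects are relieved at 1 h and five are rescued at 2, 3, 4, 5 and 6 h.

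| Time (h) | At risk | Rescued | Relieved | 1 − KM | Aalen-Johansen |
|---|---|---|---|---|---|
| 1 | 20 | 0 | 15 | 0% | 0% |
| 2 | 5 | 1 | 0 | 1 − 4/5 = 20% | 5/20 × 1/5 = 5% |
| 3 | 4 | 1 | 0 | 1 − 4/5 × 3/4 = 40% | 5% + 4/20 × 1/4 = 10% |
| 4 | 3 | 1 | 0 | 60% | 15% |
| 5 | 2 | 1 | 0 | 80% | 20% |
| 6 | 1 | 1 | 0 | 100% | 25% |

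Kaplan-Meier reports a median time to rescue of 4 h. In fact 5 of 20 were rescued, and no median is reached.

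**Other orderings of 5 rescues in 20 subjects** (Aalen-Johansen ends at 25% in each)
- All five rescues at 0.5 h, all reliefs at 1 h: 1 − KM = 5/20 = 25%. There is no overstatement.
- Rescues at 0.5, 1.5, 1.5, 3 and 3 h; reliefs 10 at 1 h, 3 at 2 h, 2 at 4 h: 1 − (19/20)(7/9)(2/4) = 63.1%.
- As in the table, but one of the 15 is relieved last, at 8 h: 1 − (5/6)(4/5)(3/4)(2/3)(1/2) = 83.3%.

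**Later attack.** With n = 10, five reliefs at 1 h and rescues at 2 to 6 h, 1 − KM is 100% against 50%.

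**Simulation.** Assumptions: constant hazards, independent latent times, continuous relief times with a latent median of 1 h (hazard ln 2 = 0.693 per hour), and a rescue hazard one third of that (0.231 per hour). The rescue share is then 0.231/(0.231 + 0.693) = 25%. Of 5,000 simulated attacks with n = 20, 58% met the trigger. Among the 990 with exactly 5 rescues, final 1 − KM averaged 64% (range 27% to 100%), and 25% of them reached 100%. Aalen-Johansen equalled the crude proportion throughout.

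**Chance that the analysis runs.** P(X ≥ 5) = 1 − Σ C(n,k) p^k (1 − p)^(n−k), summed over k = 0 to 4, at assumed true rates p:

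| p | n = 20 | n = 10 |
|---|---|---|
| 5% | 0.3% | 0.006% |
| 10% | 4.3% | 0.16% |
| 20% | 37% | 3.3% |
| 25% | 59% | 7.8% |

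**The case against.** Several objections have force.

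- **The endpoint is protected.** A reader might infer that the secondary endpoint on rescue incidence is biased. The documents do not support this. That endpoint is served by the planned count and percentage, which the censoring rule does not touch. This stands.
- **The output may never appear.** With median relief at 1.0 h, five rescues before relief may be unlikely, as the low-rate rows of the last table show. This stands as a limit on importance. It does not make the estimator right in the case where it is used.
- **No rescue curve may be printed.** SAP 7.1 promises Kaplan-Meier plots in general, but the figure list in SAP 10.1.2 has none for rescue. The point therefore concerns tabulated percentiles and intervals. The required percentage censored would also give an alert reader a warning.
- **Overstatement is not inevitable.** It needs at least one relief before a rescue, and 100% needs the last subject at risk to be rescued. It would be wrong to say that the estimate will always contradict the percentage. It can.
- **Censoring at relief is legitimate for a cause-specific hazard.** That is true, but the plan reports percentiles of time to rescue, and those depend on the relief hazard as well.
- **Subjects with neither event are not wholly ignored.** SAP 7.8.1 censors unrelieved subjects at the last symptom assessment for the relief endpoint, and SAP 10.2.10 handles rescued subjects excluded from the relief analysis. What is missing is a rule in the rescue analysis itself. The choice matters, because first-attack investigator scores stop at 6 or 8 h while rescue is counted to 48+4 h.

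**Conclusion.** The point holds as a low-severity error of method. SAP 7.8.4 states a rule that can give a wrong number: when the trigger is met, the Kaplan-Meier percentiles and intervals can make it look as if most subjects were rescued when a minority were. At the planned minimums (20 subjects, 5 rescues), the final estimate ranges from 25% to 100% against a true 25%. The 64% average rests on the assumed constant, independent hazards and 25% rescue share, and should be read as an illustration.

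Severity is low because the analysis is conditional, the study is single-arm and descriptive with no formal hypothesis testing, and the planned proportion remains correct. The documents do not support the stronger conclusion that the trial's reported rescue incidence will be wrong.

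**What to change.** In SAP 7.8.4:

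1. Replace Kaplan-Meier with the Aalen-Johansen cumulative incidence of rescue, with relief as the competing event.
2. Censor subjects with neither event at the last contact at which rescue use was ascertained, and no later than 48 + 4 = 52 h, the SAP's own rescue window. State also how unrescued subjects excluded from the relief analysis under SAP 10.2.10 are handled.
3. Add an exact 95% confidence interval to the planned n/N rescued before relief.

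Record this in SAP 8.2, which now reports no changes from the planned analyses, as a departure from protocol 10.8. The cost is one SAP edit and one program, with no new data. The drawback is that a median time to rescue will usually not be reached; when fewer than half the subjects are rescued, that is the correct result.

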#### Time to Initial Symptom Relief

The investigator will be asked to record the date and time when overall subject improvement was first noted and mark the date and time accordingly in the CRF. The time to initial symptom relief will be defined as the duration of time in hours from study drug administration until the time when overall subject improvement was first noted. Subjects not achieving the initial symptom relief will be censored at the time of their last assessment. Time to initial symptom relief will be summarized using the Kaplan-Meier method.

Analyses on time to initial symptom relief will be performed for the initial icatibant exposure and both subsequent icatibant exposures.

### 7.9 Safety Analyses

All safety summaries will be presented by icatibant exposure number, if not otherwise specified. For the initial icatibant exposure, the analyses will be presented by the pubertal status and overall; for the subsequent icatibant exposures, the analyses will be presented by the administration type (HCP Administration vs. Caregiver Administration) and overall.

All safety summaries will be presented for the initial icatibant exposure and both subsequent icatibant exposures.

All safety outcomes will be listed by subject.

#### 7.9.1 Adverse Events

Adverse events (AE) will be collected over an observation period from the time of treatment until the follow-up visit 90 ( $\pm 7$ ) days after investigational product administration (or until the event has resolved/stabilized or an outcome is reached, whichever comes first). Any serious adverse events (SAE), regardless of relationship to investigational product, which occurs in a subject after informed consent, should be recorded by the clinical site on a serious adverse event form.

AEs will be coded using MedDRA Version 16.0. A summary of subjects with treatment-emergent adverse events defined as AEs which occurred or worsened on or after the time of the first study drug administration will be presented. The summary will include the number and percentage of subjects who experience any AEs, any related AE, any severe AE, any related severe AE, any SAE, any related SAE, and any injection site reaction which was deemed an SAE; as well as the number of events in each category. Additionally, the summary table will include the number and percentage of subjects with AEs result in death.

Related AEs are AEs assessed as possibly, probably, or definitely related to the study treatment.

Treatment emergent AEs will be summarized by system organ class (SOC) and preferred term by pubertal status stratification level and icatibant exposure number. Tabulations will be presented sorted by SOC in alphabetical order and by PT within each SOC by descending frequency. The number and percentage of subjects experiencing an AE, as well as total number of AEs, will be tabulated. Treatment emergent AEs by SOC and preferred term also will be tabulated by severity and by relationship to treatment. In the case of multiple occurrences of the same AEs (at the preferred term level) in an individual subject, the AE that is classified as the most severe (i.e., maximum severity) will be identified for the analysis by severity and the AE that has the closest relationship to study drug will be identified for the analysis by relationship. Treatment emergent SAEs will be tabulated according to SOC and preferred term and provided in a data listing.

For analyses on treatment emergent AEs, in addition to summaries by icatibant exposure number, the analyses on all treatment emergent AEs by pubertal status stratification level and overall will be performed as well.

Pre-treatment AEs will be presented in a listing.

### 7.9.2 Symptoms at Injection Site

Injection site reactions (erythema, swelling, burning sensation, itching/pruritus, warm sensation, cutaneous pain) will be evaluated by the investigator or home healthcare provider/parent/legal guardian/caregiver when the subject is at the hospital/study center.

The number and percentage of subjects with any injection site reactions, and any severe reactions, will be summarized by type of reaction.

The number and percentage of subjects with injection site reactions will be summarized by maximum severity at any time point and for each study time point.

### 7.9.3 Immunogenicity

Serum samples for immunogenicity testing for determination of anti-icatibant antibodies will be collected pre-treatment and 8 and 90 days post-treatment. A subject will be considered as anti-icatibant antibody positive if he/she has at least 1 positive antibody result after the pre-treatment visit.

The number and percentage of subjects with a positive post-treatment antibody test result will be summarized.

For analyses on immunogenicity, in addition to summaries by icatibant exposure number, the analyses on all immunogenicity measurements by pubertal status stratification level and overall will be performed as well.

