10.6 Safety and Tolerability Analyses

Another key objective of the study is to investigate the safety and tolerability of a single SC dose of icatibant in pediatric subjects treated with icatibant for the first time or treated with icatibant more than once. The corresponding analyses will be based on the Safety Population.

The safety and tolerability parameters include AEs, vital signs, ECG, local tolerability at the injection site, reproductive hormone levels, immunogenicity, and standard hematology, serum chemistry, and urinalysis.

Adverse events will be categorized using the Medical Dictionary for Regulatory Activities (MedDRA) Version 16.0. The assessment of safety will be based mainly on the frequency of treatment emergent AEs. Adverse events will be summarized by system organ class (SOC) and preferred term. The number and proportion of subjects experiencing an AE will be tabulated by the stratification group and icatibant exposure number. Adverse events by SOC and preferred term also will be tabulated by severity and by relationship to treatment. In the case of multiple occurrences of the same AEs (at the preferred term level) in an individual subject, the AE that is classified as the most severe (ie, maximum severity) will be identified for the analysis by severity and the AE that has the highest relationship to investigational product will be identified for the analysis by relationship. Serious adverse events will be provided in a data listing.

Laboratory data will be listed by subject, stratification group and icatibant exposure number. Subjects with newly occurring abnormalities outside the normal range will be flagged and listed separately. Observed values and changes from pretreatment values will be summarized by the stratification group and icatibant exposure number. Shift tables will also be tabulated by stratification group, icatibant exposure number, and study time point.

Vital signs data will be listed by subject, stratification group, and icatibant exposure number. Furthermore, observed values and changes from baseline will be summarized by stratification

group and icatibant exposure number. Shift tables may be presented, utilizing reference ranges. Subjects with notably abnormal values will be identified and listed separately along with their values.

Local tolerability will be tabulated and summarized according to the type and severity of the injection site reaction.

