The impact of icatibant on the reproductive hormone levels will be assessed by presenting tabular summaries for FSH, LH, estradiol, and progesterone for females, and FSH, LH, and testosterone for males. The change from baseline values will also be summarized. Subjects with newly occurring abnormalities outside the normal range will be flagged and listed separately.

Data from other tests (eg, immunogenicity, ECG) will be listed and summarized as appropriate.

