### 7.9.7 Reproductive Hormone Assessments

Reproductive hormone levels will be measured in all subjects at pre-treatment, and 6 hours, 8 days and 90 days post-treatment for the initial icatibant treatment, and pretreatment, 8 days and 90 days post-treatment for subsequent icatibant-treated attacks. FSH, LH, estradiol, and progesterone will be summarized for females, and FSH, LH, and testosterone will be summarized for males. Observed values and changes from pre-treatment will be summarized by study time-point. The number and percentage of subjects with levels outside the normal range defined for their sex and pubertal status will be summarized by study time-point. Observations below the limit of detection will be considered abnormal if the lower limit of normal is not zero.

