**8.2 Changes from the Analyses Planned in the Protocol**

There was no change from the analyses planned in the protocol.

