#### **Baseline**

The baseline measurements for immunogenicity data for the subsequent exposures were collected every six months, regardless of the dates of icatibant exposures. Therefore, the last non-missing baseline immunogenicity measurement that was prior to a post-baseline measurement will be considered as the baseline measurement for that post-baseline measurement.

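### The SAP omits the laboratory shift tables, newly-occurring flags and vital-sign listing that Protocol 10.6 requires, and its antibody-positive rule ignores the pre-dose result

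*SAP*

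**What the plan says.** Protocol 10.6 makes these commitments for safety data:

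- Laboratory tests: "Shift tables will also be tabulated by stratification group, icatibant exposure number, and study time point". In addition, "Subjects with newly occurring abnormalities outside the normal range will be flagged and listed separately".
- Reproductive hormones: the same sentence on newly occurring abnormalities is repeated. No hormone shift table is promised.
- Vital signs: notably abnormal values are to be listed separately. Shift tables are optional.
- Immunogenicity: to be listed and summarized, with the method left open.

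The SAP handles them as follows:

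- SAP 7.9.4 counts laboratory results in five range-and-significance classes at each time point.
- SAP 7.9.7 does the like for hormones: "The number and percentage of subjects with levels outside the normal range defined for their sex and pubertal status will be summarized by study time-point".
- SAP 7.9.6 summarizes observed vital signs and changes from pre-treatment.
- SAP 7.9.3 says that antibody samples "will be collected pre-treatment and 8 and 90 days post-treatment", then sets the rule "A subject will be considered as anti-icatibant antibody positive if he/she has at least 1 positive antibody result after the pre-treatment visit" and adds "The number and percentage of subjects with a positive post-treatment antibody test result will be summarized".
- SAP 10.2.13 assigns a baseline for exposures 2 and 3: "the last non-missing baseline immunogenicity measurement that was prior to a post-baseline measurement will be considered as the baseline measurement". The rule in 7.9.3 does not refer to it.
- SAP 8.2: "There was no change from the analyses planned in the protocol".

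**The concern.** Injection site reactions, laboratory values, vital signs, reproductive hormones and antibodies are components of a primary endpoint, and the study has no control arm. The subject's own pre-dose state is therefore the main reference for judging whether a post-dose abnormality is new. A count of subjects out of range at a time point mixes those who were already out of range with those who became so. A count of antibody-positive subjects that ignores the pre-dose sample does the same.

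The study design sections single out reproductive development as the particular safety interest, so the missing flag matters most for hormones. SAP 7.9.7 also classes values below the limit of detection as abnormal whenever the lower limit of normal is not zero, which applies before dosing as much as after it.

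The SAP is also uneven: 7.9.1 uses a treatment-emergent definition for adverse events and 7.9.5 lists treatment-emergent ECG abnormalities, but no such idea is applied to antibodies, laboratory tests or hormones. Finally, a reader who relies on SAP 8.2 would believe the protocol's outputs are all present.

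**Working it through.** The plan has no figure to reproduce here. The sample of 30 is empirical, and neither document gives a rate of antibody positivity or of out-of-range values. The check is a comparison of texts, followed by an illustration on stated assumptions.

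**Step 1. Protocol 10.6 against the SAP text and output lists (SAP 10.1)**

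| Item | Protocol 10.6 | SAP | Result |
|---|---|---|---|
| Laboratory shift tables | Required | None. The only shift tables are for symptom scores (14.2.4.5 to 14.2.4.8) | Omitted |
| New laboratory abnormalities | Flag and separate listing | Listings of all abnormal values (16.2.8.2.2, 16.2.8.3.2, 16.2.8.4.2), no flag | Omitted |
| New hormone abnormalities | Flag and separate listing | Listing of all abnormal values (16.2.8.5.2), no flag | Omitted |
| Notably abnormal vital signs | Separate listing | One general listing (16.2.8.9) | Omitted |
| Hormone shift tables | Not promised | None | No departure |
| Vital-sign shift tables | Optional | None | No departure |
| Antibody summary | Method left open | Any positive result after pre-treatment | No departure, but a weak rule |

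Four commitments are missing, so SAP 8.2 is wrong as written.

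**Step 2. Why counts per time point do not replace the missing outputs**

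Suppose 3 of 30 subjects are out of range before dosing and 3 of 30 after. The SAP's summary reads 3/30 at both times. The number newly out of range could be anything from 0 (the same three subjects) to 3 (three different subjects). Only a cross-tabulation with the pre-treatment class, or a flag, tells these apart.

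**Step 3. What the antibody rule counts**

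For one exposure a subject is negative/negative, negative/positive, positive/negative or positive/positive (before/after). SAP 7.9.3 puts negative/positive and positive/positive together. Only the first is new.

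In the by-exposure tables, one subject who becomes positive after dose 1 and stays positive is 1/30 = 3% at exposure 1. If 10 subjects reach a third dose, the same subject is 1/10 = 10% at exposure 3, with no new event. SAP 10.2.13 also copies antibody results to both visits when visits are combined. When Day 90 of one exposure is combined with Day 8 of the next, a single positive sample meets the rule at both.

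**Step 4. Illustration only; the rates are assumptions**

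*Antibodies.* Let a share q of subjects be reactive before dosing and remain so, with no drug effect. Expected count = 30q; chance of at least one = 1 − (1 − q)^30.

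- q = 1%: 0.3 subjects; 1 − 0.99^30 = 26%
- q = 5%: 1.5 subjects; 1 − 0.95^30 = 79%
- q = 10%: 3.0 subjects; 1 − 0.90^30 = 96%

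Under the same assumptions, a rule limited to subjects negative before dosing counts none of them.

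*Laboratory or hormone values.* Assume a central 95% reference range, bivariate normal pre- and post-dose values with correlation ρ, and no drug effect. Out of range at a time point: 30 × 0.05 = 1.5 subjects per analyte. Newly out of range: P = 0.95 − P(in range both before and after). For the 16 chemistry and 8 haematology items there are 24 × 30 = 720 results per visit, of which 720 × 0.05 = 36 are out of range.

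| ρ | P(newly out) | Per analyte, of 30 | Of 720 results |
|---|---|---|---|
| 0 | 0.0475 | 1.4 | 34 |
| 0.5 | 0.0407 | 1.2 | 29 |
| 0.8 | 0.0281 | 0.8 | 20 |
| 0.9 | 0.0204 | 0.6 | 15 |

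The gain from a newly-occurring flag therefore depends on how stable the analyte is within a subject.

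**The case against.** The best defence is that the SAP keeps a good deal of comparison with baseline. It summarizes change from pre-treatment for laboratory tests, vital signs and hormones. It gives out-of-range percentages at pre-treatment as well as after dosing, so the two can be compared at group level. The abnormal laboratory listing shows the subject's results for that parameter at all time points. SAP 7.9.3 also calls for an analysis of all antibody measurements overall, where a persistently positive subject counts once. Protocol 7.17.1.1 makes clinically significant laboratory abnormalities adverse events, so those reach the treatment-emergent tables. All of this stands, and it narrows the gap. It does not supply the promised outputs or make SAP 8.2 correct.

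Several stronger readings do not hold:

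- A reader might infer that the antibody rule breaks the protocol. It does not, because Protocol 10.6 sets no rule for antibodies.
- A reader might infer that hormone shift tables were dropped. Only the flag and listing were promised.
- A reader might take the vital-sign omission as a lost baseline comparison. The protocol's listing is of notably abnormal values and is not defined relative to baseline.
- A reader might infer that new abnormalities appear nowhere. Those reported as adverse events do appear.
- A reader might take the 36 background results per visit as the size of the defect. By the table above, 34 or 29 of them would remain after the fix at correlation 0 or 0.5, and more than half at 0.8.

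The persistent-positivity example is also hypothetical: Protocol 1.2.2 reports that antibody positivity in adults was rare and transient.

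**Conclusion.** The point stands as two separate findings. First, four outputs that Protocol 10.6 requires are absent from the SAP, and SAP 8.2 wrongly says nothing changed. This rests on the text alone. Second, SAP 7.9.3 counts antibody positivity without regard to the pre-dose result, although that sample is collected and SAP 10.2.13 assigns a baseline for later exposures. This is a definition to improve, not a protocol departure.

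The practical loss is that new antibody positivity, and new out-of-range values that are not reported as adverse events, are isolated in no table or flag. The documents do not allow this to be sized. The illustration shows only that, with 30 subjects, a few pre-existing positives could make up the whole antibody count, and that the benefit for laboratory values is small where pre/post correlation is low. In a single-arm safety study the change should be made.

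**What to change.** 1. Add to SAP 7.9.4 and the output lists the laboratory shift tables by stratification group, exposure number and time point.
2. Add to SAP 7.9.4 and 7.9.7 a flag and separate listing for newly occurring out-of-range laboratory and hormone values. A hormone shift table is not needed to meet the protocol.
3. Add to SAP 7.9.6 the separate listing of notably abnormal vital signs, with the criterion for that label stated.
4. In SAP 7.9.3, report for each exposure the subjects negative before and positive after, positive both before and after, and never positive. Say where a subject positive before and negative after is placed, so that the groups add up. Use the SAP 10.2.13 baseline for exposures 2 and 3. Because that baseline is taken every six months whatever the dosing dates, footnote any subject whose baseline predates an earlier dose.
5. Record in SAP 8.2 any Protocol 10.6 output that is still not produced.

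The cost is SAP wording and a few standard tables and listings from data already collected. No new assessment is needed.
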